In all studies, mean HR was shown to increase by approximately 10 bpm after study drug administration, with a return to baseline by 24 hours. This rise in HR and the resulting deficiencies in standard QT heart rate correction formulae likely contribute to an artifactual calculation in the change in the QTc interval when compared to baseline. Pharmacodynamic models, where the predominant effect seen was related to HR, with no evidence of a concentration – QTc relationship, support this hypothesis.

Shift tables showed that, in this disease population, evidence of morphologic ECG abnormalities existed at baseline. In addition, the frequency of treatment emergent abnormalities was similar to the frequency of abnormal to normal transitions, particularly between dosing days. ECG changes were not associated with functional impairment.

Per current ICH E14 guidelines, the findings from these studies show that the QTc changes are below the regulatory threshold of concern, particularly considering that these studies were conducted in a target population of generally older subjects with advanced malignancies, often with significant comorbidities and concomitant medication usage. Notably, there were no absolute QTc values greater than 480 msec, no increases of \geq 60 msec and no cardiac events of torsade de pointes. One subject had a ventricular arrhythmic event, but also had evidence of intracardiac lymphoma. Therefore, based upon these data, romidepsin does not have a significant effect on the QT interval. There is a mild effect on HR that is no longer apparent 20 hours after study drug administration. Due to this effect on HR, there may be an artifactual change in the QTc interval due to the inherent inadequacy of correction formulae as the HR moves away from 60 bpm. In addition, there does appear to be a transient change in the T-wave / ST-segment in some subjects that may affect the precise determination of the T-wave in a clinical setting.

After the data cutoff date for this protocol introduction, a single report of QTc prolongation to a maximum value of 534 msec, from a minimum baseline value of 437 msec, has been reported from a subject in a clinical study of romidepsin and bortezomib for multiple myeloma. The event was reported as possibly related to romidepsin and unlikely related to bortezomib. The subject had also received ondansetron, which has been reported to prolong QTc.

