- 2.1.2.9 Clinically significant (i.e., active) cardiovascular disease: cerebral vascular accident/stroke (< 6 months prior to enrollment), myocardial infarction (< 6 months prior to enrollment), unstable angina, congestive heart failure (\geq New York Heart Association Classification Class II), congenital long QT syndrome, or other serious cardiac arrhythmia including 2nd degree atrio-ventricular (AV) block type II, 3rd degree AV block, or bradycardia (ventricular rate less than 50 beats/min).
- 2.1.2.10 Hypertrophic cardiomegaly or restrictive cardiomyopathy from prior treatment or other causes.
- 2.1.2.11 Uncontrolled hypertension, i.e., blood pressure (BP) of \geq 160/95; patients who have a history of hypertension controlled by medication must be on a stable dose (for at least one month) and meet all other inclusion criteria.
- 2.1.2.12 Triplicate average baseline QTcF interval \geq 480 ms
- 2.1.2.13 Patients taking drugs leading to significant QT prolongation (see **Appendix E**) **Note:** A 5 half-life washout period must have elapsed following the use of these drugs prior to administration of romidepsin.
- 2.1.2.14 Concomitant use of rifampin and other strong CYP3A4 inhibitors and inducers (see **Appendix C**) within 2 weeks prior to starting protocol therapy.
- 2.1.2.15 Other severe acute or chronic medical conditions including psychiatric conditions such as recent (within the past year) or active suicidal ideation or behavior; or laboratory abnormalities that may increase the risk associated with study participation or study treatment administration or may interfere with the interpretation of study results and, in the judgment of the investigator, would make the patient inappropriate for entry into this study.
- 2.1.2.16 Pregnant or lactating individuals. Pregnant individuals are excluded from this study because lenalidomide is a Class X agent with the potential for teratogenic or abortifacient effects. Because there is an unknown but potential risk for adverse events in nursing infants secondary to treatment of the participant of childbearing potential with lenalidomide, breastfeeding should be discontinued if the participant of childbearing potential is treated with lenalidomide. These potential risks may also apply to other agents used in this study.

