16.5 APPENDIX E: MEDICATIONS THAT MAY CAUSE QTc PROLONGATION

The following table presents a list of drugs that may prolong the QTc. These drugs are prohibited during the study. Romidepsin may be administered after a 5 half-life washout period elapses following the use of these drugs. Washout period is based on roughly 5 half-lives and rounded to a convenient interval.

Compound (Brand Name)	Compound Half-Life	Possible Washout Period (Hours)	Possible Washout Period (Days)
Antiarrhythmics			
Amiodarone (Cordarone, Pacerone)	58 days (15-142) 36 days (active metabolite)		180
Disopyramide (Norpace, Norpace CR)	6.7 hr (4-10)	36	
Dofetilide (Tikosyn)	10 hr	48	
Flecainide (Tambocor)	20 hr (12-27)		5
Ibutilide (Convert)	6 hr (2-12) (variable among patients)	36	
Procainamide (Pronestyl, Procanbid, Procan)	3-4 hr for PA and NAPA (active metabolite)	24	
Quinidine (Quinaglute, Cardioquin, Quinidex)	6-8 hr in adult; 3-4 hr in children	36	
Sotalol (Betapace, Sorine)	12 hr	72	
Antibiotics			
Clarithromycin (Biaxin, Biaxin XL)	Nonlinear PK 3-4 hr (250 mg Q12) 5-7 hr (500 mg Q12)	36	
Erythromycin (Benzamycin, Eyc, E-glades, Erygel, E-solve 2, Akne-Mycin, Eryderm, Sansac, Erythro-Statin, Erymax, Staticin, T-Stat, C-solve-2, Erycetter, PCE, Ery-Tab, E-Mycin, E-Base, E.E.S., Eryped, E.E.S 200, E.E.S 400, Pediamycin, Eryzole, Erythrocin)	Each salt form has different half-life		
Gatifloxacin (Tequin, Tequin Teqpaq)	7-14 hr	48	
Grepafloxacin (Raxar)	16 hr		3
Antibiotics (cont'd)			
Levofloxacin (Levaquin, Quixin, Elequin)	6-8 hr	48	
Moxifloxacin (Avelox, Vigamox)	12 ± 1.3 hr	72	
Sparfloxacin (Zagam)	20 hr (16-30)		4
Telithromycin (Ketex)	2-3 hr	24	
Anticonvulsants			
Felbamate (Felbatol)	20-23 hr		5
Fosphenytoin (Cerebyx)	12-29 hr		6
Antidepressants			
Venlaflaxine (Effexor)	5 ± 2 hr for parent comp. 11± 2 hr for OVD (active metabolite)	60	
Antidiarrheals			
Octreotide (Sandostatin)	1.7 hr	12	

Compound (Brand Name)	Compound Half-Life	Possible Washout Period (Hours)	Possible Washout Period (Days)
Antiemetics			
Dolasetron (Anzemet)	8.1 hr		
Droperidol (Inapsin)	2.2 hr	10	
Domperidone (Motilium)	7-8 hr	48	
Palonosetron (Aloxi)	40 hr		10
Antihypertensives			
Moexipril/Hydrochlorothiazide (Uniretic)	2-9 hr(include active metabolite) for moexipril; 5.6-14.8 hr for HCTZ	48	
Antimalarials			
Halofantrine (Halfan)	6-10 days (variable among individuals)		45
Quinidine (Quinaglute, Cardioquin, Quinidex)	6-8 hr in adult; 3-4 hr in children	36	
Antimanics			

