Lithium (Eskalith, Lithobid, Lithonate)	24 hr (10-50)		7
Antineoplastics			
Arsenic trioxide (Trisenox)	Not characterized		
Tamoxifen (Nolvadex)	5-7 days (biphasic)		30
Antiprotozoals			
Pentamidine (NebuPent, Pentam)	6.4 ± 1.3 hr	36	
Antipsychotic agents			
Chlorpromazine (Thorazine)	30 ± 7 hr		7
Haloperidol (Haldol)	18 ± 5 hr		5
Mesoridazine (Serentil)	24-48 hr (animal study)		10
Pimozide (Orap)	55 hr		14
(Continued from previous page)			
Antipsychotic agents (cont'd)			
Quetiapine (Seroquel)	6 hr	36	
Risperidone (Risperdal, Risperdal Consta)	3-20 hr (extensive to poor metabolizer) 9-hydroxyrisperidone (active metabolite) $T_{1/2} = 21-30$ hr (extensive to poor metabolizer)		4
Thioridazine (Mellaril)	20-40 hr (Phenothiazines)		7
Ziprasidone (Geodon, Zeldox)	7 hr	36	
Antispasitics			

Compound (Brand Name)	Compound Half-Life	Possible Washout Period (Hours)	Possible Washout Period (Days)
Tizanidine (Zanaflex)	2.5 hr	12	
Antivirals			
Amantadine (Symadine, Symmetrel)	17 ± hr (10-25)		4
Foscarnet (Foscavir)	87.5 ± 41.8 hr (distribution and release from bone)		20
Analgesics			
Levomethadyl (Orlaam)	Multiple compartment PK with active metabolite 2.6 day for LAAM, 2 day for nor-LAAM, 4 day for dinor-LAAM		20
Asthma medications			
Salmeterol (Advair Diskus, Serevent, Serevent Diskus)	5.5 hr (only one datum)	36	
Calcium channel blockers			
Bepridil (Vascor)	42 hr (26-64)		10
Isradipine (DynaCirc)	8 hr (multiple metabolites)	48	
Nicardipine (Cardene)	~2 hr post IV infusion	12	
Cholinergic enhancers			
Cisapride (Propulsid)	6-12 hr, up to 20 hr	60	
Diuretics			
Indapamide (Lozol)	14 hr (biphasic elimination)		3
Immunosuppressants			
Tacrolimus (Prograf, Protopic)	~34 hr in healthy patients ; ~19 hr in kidney transplant		7
Migraine medications			
Naratriptan (Amerge)	6 hr	36	
Sumatriptan (Imitrex)	2.5 hr	12	
Zolmitriptan (Zomig)	2.8-3.7 hr (higher in female)	18	
Narcotic pain relievers			
Methadone (Dolophine, Methadose)	15-30 hr		7
Sedatives			
Chloral hydrate	Readily converted to Trichloroethanol (active metabolite $T_{1/2} = 7-10$ hour)	48	

Abbreviated Title: *RAdR for R/R TCM*

Version Date: 12/04/2025

References:

Physician's Desk Reference 2002

Facts and Comparisons (update to June, 2000)

The Pharmacological Basis of Therapeutics 9th Edition, 1996

Abbreviated Title: RAdR for R/R TCM

Version Date: 12/04/2025

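### Appendix E's 180-day amiodarone washout is only 3.1 half-lives of the parent drug; the protocol's own 5 half-life rule gives 290 days

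*Combined protocol and SAP*

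**What the plan says.** Section 2.1.2.13 excludes patients taking drugs that significantly prolong QT, refers to Appendix E for the list, and adds the condition "A 5 half-life washout period must have elapsed following the use of these drugs prior to administration of romidepsin". Appendix E (Section 16.5) repeats the rule: "Romidepsin may be administered after a 5 half-life washout period elapses following the use of these drugs". It then explains how its figures were obtained: "Washout period is based on roughly 5 half-lives and rounded to a convenient interval".

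The amiodarone row gives the half-life as "58 days (15-142) 36 days (active metabolite"). The first figure is the parent drug with its range; the second is the metabolite. The washout entered is 180 days, in a column headed as a possible washout period in days.

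Two other rows show how the table treats a drug with several active components:

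- **Levomethadyl** lists "2.6 day for LAAM, 2 day for nor-LAAM, 4 day for dinor-LAAM", with a washout of 20 days.
- **Venlafaxine** lists 5 h for the parent and 11 h (± "2 hr for OVD (active metabolite")) for the metabolite, with a washout of 60 h.

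**The concern.** The criterion and the table should lead to the same decision, and for amiodarone they do not. A washout meant to clear a drug with two active components has to be set by the slower one. The 180 days matches the faster one exactly, which suggests that the wrong half-life was multiplied by five.

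Section 2.1.2.13 sends the person screening a patient to this table, so the cell works as an eligibility threshold. A patient 180 to 290 days after the last amiodarone dose passes on the table and fails on the criterion.

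The washout applies at the first romidepsin dose. That dose falls in the cycle where ondansetron or granisetron premedication is mandatory (Section 3.4.2, Table 4), and Section 1.5.1.5 links a significant part of the QTcF change seen with romidepsin to antiemetics. The Study Calendar (Section 3.9) schedules the ECG at screening only, with later tests as clinically indicated. Entry rules therefore carry much of the QT protection.

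**Working it through.** **Inputs**, all from Appendix E unless noted:

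- Rule: 5 half-lives (also Section 2.1.2.13).
- Amiodarone parent half-life: 58 days, range 15 to 142.
- Amiodarone active metabolite half-life: 36 days.
- Listed amiodarone washout: 180 days.

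**Step 1. Reproduce the listed figure.** Washout = 5 x half-life.

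- From the metabolite: 5 x 36 = 180 days. This matches exactly.
- From the parent: 5 x 58 = 290 days. This does not match.

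**Step 2. Size of the gap.**

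- Half-lives of the parent covered: 180/58 = 3.10.
- Shortfall: 290 - 180 = 110 days; 110/290 = 37.9%.
- Parent drug remaining, assuming simple exponential elimination at the 58-day half-life: 2^(-3.10) = 11.6% at 180 days, against 2^(-5) = 3.1% at five half-lives.
- At the upper listed half-life: 180/142 = 1.27 half-lives.

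**Step 3. Could rounding explain it?** Seven other rows print a central half-life with a range, as amiodarone does. Dividing each washout by the central value and by the upper value:

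| Drug | Washout | Washout / central | Washout / upper |
|---|---|---|---|
| Sparfloxacin | 4 d = 96 h | 96/20 = 4.80 | 96/30 = 3.20 |
| Disopyramide | 36 h | 36/6.7 = 5.37 | 36/10 = 3.60 |
| Amantadine | 4 d = 96 h | 96/17 = 5.65 | 96/25 = 3.84 |
| Bepridil | 10 d = 240 h | 240/42 = 5.71 | 240/64 = 3.75 |
| Ibutilide | 36 h | 36/6 = 6.00 | 36/12 = 3.00 |
| Flecainide | 5 d = 120 h | 120/20 = 6.00 | 120/27 = 4.44 |
| Lithium | 7 d = 168 h | 168/24 = 7.00 | 168/50 = 3.36 |
| **Amiodarone (parent)** | 180 d | 180/58 = **3.10** | 180/142 = **1.27** |

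The seven comparators run from 4.8 to 7.0 at the central value and from 3.0 to 4.4 at the upper value. Six of the seven fall below 4 at the upper value, so the table evidently aims at central half-lives. Amiodarone is lowest on either reading.

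**Step 4. Which component does the table use?**

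- Levomethadyl: 20/4 = 5.0 half-lives of the longest-lived component.
- Venlafaxine: 60/11 = 5.5 half-lives of the longer-lived metabolite (60/5 = 12 for the parent).

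Both follow the slowest component. Amiodarone follows the fastest.

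**The case against.** The arithmetic is not in dispute. The strongest case on the other side is about weight.

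- **The binding rule is right.** Five half-lives is stated correctly twice. The 180 sits in a column labelled as a possible period, and the 58-day figure is in the same row, so a careful reader can recompute. This stands and limits the harm, but the criterion refers the reader to this table, and a printed number of days is what will usually be applied.
- **The table is loose elsewhere.** The longest-component convention is not written down and rests here on two rows. Risperidone, which lists a 21 to 30 h metabolite ("9-hydroxyrisperidone (active metabolite")), gets 4 days: 96/30 = 3.2 to 96/21 = 4.6 half-lives. Cisapride gives 60/20 = 3.0 at its upper value. These rows weaken any claim of a uniform standard. They fall near 3 only at the upper end of a range, however; amiodarone does so at its central value. Risperidone prints no central metabolite half-life, and at 21 h its 4 days could pass as rounding.
- **290 days is itself a choice.** Over the listed range of 15 to 142 days, five half-lives spans 75 to 710 days. True, but the central value is what the comparable rows use.
- **The consequence is slight.** Baseline QTcF of 480 ms or more, congenital long QT and serious arrhythmia are excluded separately in Section 2.1.2. Section 1.5.1.5 concludes that "romidepsin does not have a significant effect on the QT interval", and the mean QTcF increases it reports are 2.7 and 5 msec. Twenty patients had been enrolled when the design changed (Section 3.4.1). Against the 30 or 36 printed in Section 10.2, that left 10 to 16 still to enrol. This stands in full.

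**Conclusion.** The amiodarone entry is wrong as written. It gives 3.1 half-lives of the parent drug where the protocol requires 5: 180 days against 290, a shortfall of 110 days or 38%. The wording about approximate half-lives and convenient intervals does not reach that far, since 180 is an exact multiple of the other half-life in the row.

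The conclusion rests on reading the rule at the listed central half-life of the longest-lived listed component, which is how the levomethadyl and venlafaxine rows behave. The 11.6% residual also assumes simple exponential elimination.

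The practical importance is limited. The documents give no frequency of prior amiodarone use; only patients who stopped it 180 to 290 days earlier are touched, and they are likely to be very few. No endpoint, analysis or sample size is affected. It is still a safety threshold that contradicts its own rule, and it should be corrected.

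**What to change.** In Appendix E, change the amiodarone washout from 180 to about 290 days. Add one sentence saying that washouts are calculated from the longest-lived listed active component at its central half-life, so that the table and Section 2.1.2.13 give the same answer.

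The cost is one table cell and one sentence in the next amendment. A very few patients with amiodarone use 180 to 290 days earlier would have to wait or would be ineligible. Given the rapid progression described in Section 1.10.2, waiting may in practice mean exclusion, but Section 2.1.2.13 already requires that at the listed central half-life.

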16.6 APPENDIX F: STUDY DRUG DIARY

Study Drug Diary

Patient Initials:		Principal Investigator: [name]
Patient Study ID #:		Research Nurse:
Drug Doses:	Lenalidomide (days 1-10): _____ CC-486 (5-azacitidine): _____	Cycle #: _____

Instructions:

- Use this diary to record all doses of oral study medication taken.
- You should bring this study drug diary and each of your study medications (including leftover pills and empty bottles) with you to each clinic visit.
- On clinic days, oral medications must be brought with you and taken in clinic.
- Contact us if you have any side effects or before starting any new medications or over-the-counter drugs.
- If you have questions at any time, please contact your doctor or nurse.

Study Drugs:

The study medications should be taken as follows, the dose of each will be assigned to you by your doctor:

Lenalidomide capsules should be taken with a glass of water with or without food
Dexamethasone tablets will be given in clinic and taken by mouth (PO)
CC-486 (5-azacitidine) capsules should be taken with a glass of water with or without food
Romidepsin is given by IV, in the clinic

Additional Information:

- Each of the study drugs should be taken at about the same time each day, with or without food as described above
- If you do not remember to take all or any of the medications on any day, please tell us. Do not make-up the dose or take extra the following day to make-up for the missed dose.
- If you vomit after taking a dose, you should not take another dose that day.
- Lenalidomide and CC-486 (5-azacitidine) are to be administered orally once daily. The capsules are to be taken around the same each day with (8 ounces of water). The capsules must be swallowed whole and may be taken with or without food. If a dose is not taken at the scheduled time and it has been less than 12 hours since the regularly scheduled time, it can be taken as soon as possible on the same day. If it has been more than 12 hours, skip the missed dose but take the next dose at the normal time on the following day. Do not take extra doses to make up the missed dose. Do not take 2 doses at the same time.
- Patients who are not already on prophylactic or therapeutic doses of anticoagulants will be given aspirin 81mg to be taken by mouth daily
- Patients will be given ondansetron 8mg by oral or by IV to prevent chemotherapy-associated nausea on Days 1 and 10 (may be omitted during cycles 2-6 per doctor's instructions)

Study Drug Diary:

Please record the dose/number of pills of each study drug taken in the table below:

Cycle Day	Date	Lenalidomide/ Revlimid®		CC-486 (5-Azacitidine)		Dexamethasone	Romidepsin	Comments (Please note reason if dose is missed)
		#/ Dose Taken	Time	#/ Dose Taken	Time			
1						PO in clinic	IV in Clinic	
2								
3								
4								
5								
6								
7								
8								
9								
10						PO in clinic	IV in Clinic	
11-28								

STAFF USE ONLY

Date returned/reviewed: _____

Staff member: _____

Notes/Comment
